### **2.1.1 General definitions**

**Investigational drug** refers to ruxolitinib and **study treatment** refers to ruxolitinib or placebo.

### **2.1.2 Date of first administration of study treatment in treatment period 1**

The date of first administration of study treatment is defined as the first date when a nonzero dose of study treatment was administered and recorded on DAR TRT1 eCRF. The date of first administration of study treatment in period 1 will also be referred as the *start date of study treatment*.

### **2.1.3 Date of last administration of study treatment in treatment period 1**

The date of last administration of study treatment is defined as the last date when a nonzero dose of study drug was administered and recorded on DAR TRT1 eCRF.

### **2.1.4 Date of first administration of open label ruxolitinib in treatment period 2**

The date of first administration of open label ruxolitinib in treatment period 2 is defined as the first date when a nonzero dose of open label ruxolitinib was administered and recorded on DAR TRT2 (ruxolitinib) eCRF.

### 2.1.5 Date of last administration of open label ruxolitinib in treatment period 2

The date of last administration of open label ruxolitinib in treatment period 2 is defined as the last date when a nonzero dose of study drug was administered and recorded on DAR TRT2 eCRF.

### 2.1.6 Last date of study treatment

The last date of study treatment is defined as (1) the date of last administration of study treatment in treatment period 1 if the patient never went to treatment period 2 or (2) the date of last administration of study treatment in treatment period 2 if the patient went to treatment period 2.

### 2.1.7 Study day

The term assessment will be used to represent an evaluation, a measurement or an event (e.g. AE onset, laboratory abnormality occurrence, disease progression, etc)

The study day *for efficacy assessments* will be calculated as follows:

Study day = date of assessment – randomization date + 1  
*if date of assessment is after the randomization date.*

Study day = date of assessment – randomization date  
*if date of assessment is before the randomization date.*

The study day *for safety assessments* will be calculated as follows:

Study day = date of assessment – start date of study treatment + 1  
*if date of assessment is after the randomization date.*

Study day = date of assessment – start date of study treatment  
*if date of assessment is before the randomization date.*

For any assessment or events such as baseline disease characteristics or medical history (e.g., time since diagnosis of disease) that is supposed to occur prior to randomization/start date of the study treatment, study day will be negative. There is no Day 0 defined.

### Time unit

A year length is defined as 365.25 days. A month length is 30.4375 days (365.25/12). If duration is reported in months, duration in days will be divided by 30.4375. If duration is reported in years, duration in days will be divided by 365.25.

### 2.1.8 Baseline

Baseline values for safety and non-safety evaluations are defined as below unless specified otherwise in the RAP.

For *safety evaluations* (e.g. laboratory and vital signs), the last assessment available before or on the start date of study treatment in period 1 (only if such assessment are pre-dose) is taken as a “baseline” assessment.

For *efficacy and other non-safety evaluations* (e.g. MRI / CT scan), the last available assessment before or on the day of randomization is taken as the “baseline” value or “baseline” assessment. Multiple assessments on the same day are not expected.

If patients have no assessments as defined above, the baseline result will be missing.

### 2.1.9 Last contact date

The last contact date will be derived for patients not known to have died at the analysis cut-off using the latest complete date among the following:

- Date of randomization
- Last contact date/last date patient was known to be alive from the Survival Follow-up page (if patients status is alive)
- Assessment dates (i.e. vital signs assessment, performance status assessment, and assessment date for spleen imaging, central laboratory, completed PROs)
- Start/end dates from drug administration records and for further antineoplastic therapies
- Adverse events dates including the start and stop date of AEs
- Date of discontinuation from ‘End of Treatment’ eCRF

The last contact date is defined as the latest complete date from the above list on or before the cut-off date. The cut-off date will not be used for last contact date, unless the patient was seen or contacted on that date. No date post cut-off date will be used.

### 2.1.10 Windows for multiple assessments

In order to summarize data collected over time (including unscheduled visits), the assessments will be time slotted. The following general rule will be applied in creating the assessment windows: If more than one assessment is done within the same time window, the assessment performed closest to the target date will be used. If 2 assessments within a time window are equidistant from the target date, then the later of the 2 assessments will be used. Data from all assessments (scheduled and unscheduled), including multiple assessments, will be listed.

**Table 2-1 Time windows for imaging assessments**

Time Window	Planned Visit Timing	Time Window Definition
Screening	Study Days -7 to -1*	Study Days -7-1
Week 12	Study Day 84	Study Days 81-87
Week 24	Study Day 168	Study Days 161-175
Week 36	Study Day 252	Study Days 245-259
Week 48	Study Day 336	Study Days 329-343
Every 12 weeks thereafter		
Week $y=48+12*k$ (with $k = 1, 2, \dots$ )	Study Day $(48+12*k)*7$	Study Day Study Day $(48+12*k)*7 - 7$ to Study Day $(48+12*k)*7 + 7$ Note: EOT data visit are included if obtained within 30 days of last non-zero dose

intake.

\*Study Day 1 = randomization date

The visits and time windows apply to treatment period 1, 2 and post-treatment follow up, i.e. week 48 visit will be in the same window of 329-343 days in all these periods.

**Table 2-2 Time windows for laboratory and spleen palpation assessments**

Time Window	Planned Visit Timing	Time Window Definition
Baseline (Day 1)	On Study Day 1*	Study Days -40-1
Week 4	Study Day 28	Study Days 25-31
Week 8	Study Day 56	Study Days 49-63
Week 12	Study Day 84	Study Days 81-87
Week 16	Study Day 112	Study Days 105-119
Week 20	Study Day 140	Study Days 133-147
Week 24	Study Day 168	Study Days 161-175
Week 32	Study Day 224	Study Days 217-231
Week 36	Study Day 252	Study Days 245-259
Week 48	Study Day 336	Study Days 329-343
Every 12 weeks thereafter		
Week $y=48+12*k$ (with $k = 1, 2, \dots$ )	Study Day $(48+12*k)*7$	Study Day Study Day $(48+12*k)*7 - 7$ to Study Day $(48+12*k)*7 + 7$ Note: EOT data visit are included if obtained within 30 days of last non-zero dose intake.

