Visit Name	Category	Protocol Section	Molecular Pre-screening	Screening	Treatment Period 1 (Blinded)											End of treatment (EOT)	Progressive disease (PD) confirmation	Safety Follow up 30 days after last dose	Post treatment follow up (See Section 7.1.7)	Survival Follow up (Every 3 months)
					Day 1	Week 4	Week 8	Week 12	Week 16	Week 20	Week 24	Week 32	Week 36 (MRI / CT)	Week 40	Week 48+ (every 12 weeks until EOT)					
Day				-40 to -1	1	28	56	84	112	140	168	224	252	280	336+					
Visit window (Study day)						+/-3	+/-3	+/-3	+/-3	+/-3	+/-7	+/-7	+/-7	+/-7	+/-7					
Physical examination	S	7.2.2.1		x	x	x	x	x	x	x	x	x		x	x	x				
Performance status	D	7.2.2.4		x	x	x	x	x	x	x	x	x		x	x	x				
Height	D	7.2.2.3		x																
Weight	D	7.2.2.3		x	x	x	x	x	x	x	x	x		x	x	x				
Vital signs	D	7.2.2.2		x	x	x	x	x	x	x	x	x		x	x	x				
Spleen measurement (length)	D	7.2.2.1		x	x	x	x	x	x	x	x	x		x	x	x				
Laboratory assessments		7.2.2.5																		
Hematology	D	7.2.2.5.1		x	x	x	x	x	x	x	x	x		x	x	x	x (Refer to PD guidance)		x	
Chemistry	D	7.2.2.5.2		x	x	x	x	x	x	x	x	x		x	x	x				

[figure not shown]
Visit Name	Category	Protocol Section	Molecular Pre-screening	Screening	Treatment Period 1 (Blinded)											End of treatment (EOT)	Progressive disease (PD) confirmation	Safety Follow up 30 days after last dose	Post treatment follow up (See Section 7.1.7)	Survival Follow up (Every 3 months)
					Day 1	Week 4	Week 8	Week 12	Week 16	Week 20	Week 24	Week 32	Week 36 (MRI / CT)	Week 40	Week 48+ (every 12 weeks until EOT)					
Day				-40 to -1	1	28	56	84	112	140	168	224	252	280	336+					
Visit window (Study day)						+/-3	+/-3	+/-3	+/-3	+/-3	+/-7	+/-7	+/-7	+/-7	+/-7					
Coagulation	D	7.2.2.5.4		x	x (To be performed as clinically indicated)											x				
Urinalysis	D	7.2.2.5.3		x													x			
Pregnancy test	D	7.2.2.5.5		x	x	x	x	x	x	x	x			x	x		x			
Hepatitis test	D	7.2.2.5		x																
Imaging		7.2.1																		
ECG	D	7.2.2.6.1		x	x (Every 48 weeks)											x				
MRI/CT	D	7.2.1		x (-7 to -1)				x			x		x		x		x			
Safety		7.2.2																		
Adverse events	D			x	x (at every visit)															

[figure not shown]
Visit Name	Category	Protocol Section	Molecular Pre-screening	Screening	Treatment Period 1 (Blinded)										End of treatment (EOT)	Progressive disease (PD) confirmation	Safety Follow up 30 days after last dose	Post treatment follow up (See Section 7.1.7)	Survival Follow up (Every 3 months)

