7.1.4 Treatment Period

Treatment Period 1

Blinded study treatment will be initiated on Day 1 after randomization and treatment assignment by IRT system. Day 1 is defined as the first day of study treatment. After day 1, visits will occur at the following frequency as specified in Table 7-1.

- Every 4 weeks until week 24 (+/- 3 days)
- Every 8 weeks until week 48 (+/- 7 days)
Note: Week 36 visit is required only for MRI/CT of the spleen.
- Every 12 weeks until the end of treatment (+/- 7 days)

Blinded treatment will be administered until disease progression or patient discontinuation.

Treatment Period 2

[figure not shown]
Patients progressing due to splenomegaly or symptom (MF-7 score) in Treatment Period 1 will enter the ruxolitinib Treatment Period 2. All patients are required to have an End of Treatment Period 1 assessment prior to entering Treatment Period 2. All End of Treatment Period 1 assessments should be performed within 2 weeks prior to the first dose of ruxolitinib in Treatment Period 2. The End of treatment bone marrow biopsy and MRI/CT assessments should follow the schedule as per Section 7.2.1.1. The schedule of assessments for patients entering Treatment Period 2 will continue from when the patient discontinued in Treatment Period 1 (Table 7-1 [B]).

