## **2.5 Analysis of the primary objective**

The study was terminated prematurely with insufficient sample size and study duration to evaluate the effect of ruxolitinib in delaying progression of MF from early disease to more advanced disease stages. Therefore, the initial primary end point, progression free survival

(PFS), will not be derived and no statistical hypothesis will be tested. Consequently, no supportive analysis for per protocol set is planned.

The early terminated study aims to present data collected for the endpoints of interest, including change in spleen volume and length from baseline, change in symptoms using MF-7 and EQ-5D from baseline (see patient reported outcomes section), safety endpoints [REDACTED]. Descriptive statistics will be used to summarize the endpoints of interest and the FAS will be used for analyzing the data. Change in spleen volume and palpable spleen length below costal margin

Regular assessments of spleen volumes via Magnetic Resonance Imaging (MRI) or Computed Tomography (CT) are performed to evaluate progressive splenomegaly. Spleen size is assessed by palpation and measured in centimeters using a soft ruler, from the costal margin to the point of greatest splenic protrusion.

Spleen volume, spleen length, absolute change and percentage change in spleen volume by MRI/CT and palpable spleen length below costal margin will be summarized descriptively by treatment for each assessment timepoints.

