### **2.8.3 Laboratory data**

Laboratory, data summaries will include all assessments available for the lab parameter collected no later than 30 days after the last study treatment administration date, using data from all sources (central and local laboratories). All laboratory assessments will be listed and those collected later than 30 days after the last study treatment date will be flagged in the listings.

Grade categorization of lab values will be assigned programmatically as per NCI Common Terminology Criteria for Adverse Events (CTCAE) version 4.03. The calculation of CTCAE grades will be based on the observed laboratory values only, clinical assessments will not be taken into account. The criteria to assign CTCAE grades are given in <Novartis internal criteria for CTCAE grading of laboratory parameters>. The latest available version of the document based on the underlying CTCAE version 4.03 at the time of analysis will be used. The Novartis internal CTCAE grading document will be added as appendix to the CSR.

For laboratory tests where grades are not defined by CTCAE v4.03, results will be graded by the low/normal/high (or other project-specific ranges, if more suitable) classifications based on laboratory normal ranges.

A severity grade of 0 will be assigned for all non-missing lab values not graded as 1 or higher. Grade 5 will not be used. For laboratory tests that are graded for both low and high values,

summaries will be done separately and labelled by direction, e.g., sodium will be summarized as hyponatremia and hypernatremia.

In rare cases where multiple lab measurements meet the baseline definition, with no further flag or label that can identify the chronological order then the following rule should be applied: If values are from central and local laboratories, the value from central assessment should be considered as baseline. If multiple values are from the same laboratory (local or central) then the value with the last sequence/repeat number should be considered as baseline.

A listing of laboratory values will be provided by laboratory test, patient, and study day. A separate listing will display notable laboratory abnormalities (i.e., newly occurring CTCAE grade 3 or 4 laboratory abnormalities).

The following by-treatment summaries will be generated separately for hematology and biochemistry laboratory tests:

- shift tables using CTCAE grades to compare baseline to the worst on-treatment value

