- for laboratory tests where CTCAE grades are not defined, shift tables using the low/normal/high/(low and high)
- listing of all laboratory data with values flagged to show the corresponding CTCAE grades and the classifications relative to the laboratory normal ranges.
- Boxplots of hematological parameters (hemoglobin and platelet count) over time

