**Table 5-2 Visit evaluation schedule in respect to the components of the primary endpoint**

**A) Treatment Period 1 (Blinded)**

Visit Name	Category	Molecular Pre-screening	Screening	Treatment Period 1 (Blinded)											End of treatment (EOT)	Progressive disease (PD) confirmation	Safety Follow up 30 days after last dose	Post treatment follow up	Survival Follow up (Every 3 months)
				Day 1	Week 4	Week 8	Week 12	Week 16	Week 20	Week 24	Week 32	Week 36 (MRI / CT)	Week 40	Week 48+ (every 12 weeks until EOT)					
Day			-40 to -1	1	28	56	84	112	140	168	224	252	280	336+					
Visit window (Study day)					+/-3	+/-3	+/-3	+/-3	+/-3	+/-7	+/-7	+/-7	+/-7	+/-7					
Hematology	D		x	x	x	x	x	x	x	x	x		x	x	x	x		x	
MRI/CT	D		x (-7 to -1)				x			x		x		x	x			x	
Bone Marrow biopsy and aspirate	D		x	x (every 2 years)											x			x	
MF-7	D		x	x	x	x	x	x	x	x	x		x	x	x	x	x	x	

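### SAP Table 2-2 gives laboratory and spleen palpation data a Week 36 window, when neither is scheduled, and no Week 40 window, when both are

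*SAP*

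**What the plan says.** SAP 2.1.10 sets the rule: "In order to summarize data collected over time (including unscheduled visits), the assessments will be time slotted". Two tables implement it. Table 2-1 covers imaging, and "Table 2-2 Time windows for laboratory and spleen palpation assessments" covers the rest of what matters here. After Week 24, the Table 2-2 rows are Week 32, Week 36, Week 48 and then every 12 weeks. There is no Week 40 row.

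The visit schedule differs:

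- Protocol 7.1.4 has visits every 8 weeks from Week 24 to Week 48, with a note that the "Week 36 visit is required only for MRI/CT of the spleen".
- Protocol Table 7-1 (A) marks hematology, chemistry and the row beginning "Spleen measurement (length" at Weeks 32, 40 and 48+. All three are blank at Week 36.
- SAP 1.1 repeats the 8-weekly visits. SAP Table 5-2, titled "Visit evaluation schedule in respect to the components of the primary endpoint", marks hematology at Week 40 (Day 280) and leaves Week 36 blank.

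Two planned outputs use these data by time. SAP 2.5 says that "palpable spleen length below costal margin will be summarized descriptively by treatment for each assessment timepoints", and SAP 2.8.3 plans "Boxplots of hematological parameters (hemoglobin and platelet count) over time".

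**The concern.** Table 2-2 contradicts both the protocol schedule and the SAP's own Table 5-2. Its Week 36 row has the same target day and limits as the Week 36 row of Table 2-1. That row is right for imaging but does not fit data that are not collected at that visit. SAP section 4 declares no change to the protocol-specified analyses, so nothing marks the difference as intended.

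A programmer who applies the slotting rule literally finds no timepoint for a Week 40 laboratory or palpation value taken exactly on schedule. The value then drops out of any display built by timepoint. The table also defines a Week 36 timepoint that only unscheduled or off-schedule values can fill. After early termination the planned output consists of descriptive summaries and listings, and change in palpated spleen size is one of the endpoints of interest in SAP Table 1-1.

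**Working it through.** **Inputs.** Visit days and allowed deviations come from Protocol Table 7-1 (A): ±3 days through Week 20 and ±7 days from Week 24. Analysis windows come from SAP Table 2-2.

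**Method.** On-schedule days for a visit are target day ± allowed deviation. Count how many of these days lie inside any Table 2-2 window.

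| Visit | On-schedule days | Table 2-2 window | Days covered |
|---|---|---|---|
| Week 4 | 25-31 | 25-31 | 7 of 7 |
| Week 8 | 53-59 | 49-63 | 7 of 7 |
| Week 12 | 81-87 | 81-87 | 7 of 7 |
| Week 16 | 109-115 | 105-119 | 7 of 7 |
| Week 20 | 137-143 | 133-147 | 7 of 7 |
| Week 24 | 161-175 | 161-175 | 15 of 15 |
| Week 32 | 217-231 | 217-231 | 15 of 15 |
| Week 40 | 273-287 | none | 0 of 15 |
| Week 48 | 329-343 | 329-343 | 15 of 15 |

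**Distance to the neighbouring windows.**

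- The Week 36 window ends on Day 259. Week 40 days lie 273 − 259 = 14 to 287 − 259 = 28 days after it.
- The Week 48 window starts on Day 329. The latest on-schedule Week 40 day is 329 − 287 = 42 days before it.
- Table 2-2 has no window from Day 260 through Day 328, so a Week 40 value cannot be slotted to either neighbour.

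**The Week 36 row.** No on-schedule laboratory or palpation day lies in Days 245-259. The nearest are Day 231 (245 − 231 = 14 days before the window) and Day 273 (273 − 259 = 14 days after it).

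**Spacing on the displays.** On-schedule data go from Day 224 to Day 336, which is 336 − 224 = 112 days. The schedule gives 280 − 224 = 56 days and then 336 − 280 = 56 days.

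**With a Week 40 row (Days 273-287) in place of Week 36.** All 15 Week 40 days are covered and 9 of 9 visits are fully covered. The new window overlaps neither Days 217-231 nor Days 329-343.

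**Other routes into a window.** The note in the last row of Table 2-2 admits end-of-treatment data obtained within 30 days of the last dose. It does not cover a routine Week 40 visit.

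**The case against.** The strongest reply concerns the consequence, since the mismatch itself is plain.

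- The SAP does not say what happens to values that match no window, so their loss from the displays is an inference. This is correct as far as it goes. But SAP 2.1.10 makes slotting the way data are summarized over time and offers no fallback to the nominal visit, so a value without a window has no timepoint to appear under.
- SAP 2.8.3 says laboratory summaries include all assessments up to 30 days after the last dose. That sentence sets a date limit and assigns no timepoint, so it does not place a Week 40 value on a boxplot over time. It does not apply to spleen length at all.
- The windows in Table 2-2 have gaps throughout, so any value outside them meets the same silence. This is true, but the other gaps catch only off-schedule values. Week 40 is the one scheduled visit through Week 48 that is lost when patients attend on time.
- Removing the Week 36 row takes away a slot from unscheduled values on Days 245-259. This stands as a small cost. Those values remain in the listings, and no scheduled laboratory or palpation visit can fall there.
- The practical weight is low. PFS is not derived, no hypothesis is tested, and SAP 1.2 calls the numbers randomized and the study duration minimal. This stands and is why the point is minor.

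**Conclusion.** The point holds and is minor. Table 2-2 is wrong as written: it covers eight of the nine laboratory and palpation visits scheduled from Week 4 through Week 48, and covers Week 40 on none of its 15 allowed days.

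The affected outputs are the by-timepoint summary of palpable spleen length and the hemoglobin and platelet boxplots. Three outputs are unaffected. The listings carry every assessment. The "shift tables using CTCAE grades to compare baseline to the worst on-treatment value" do not depend on visit windows. Spleen volume uses Table 2-1, where Week 36 is correct.

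The conclusion assumes that the slotting rule is applied as written and that values without a window are not shown under a timepoint. How much data is lost cannot be stated, because the documents do not say how many patients reached Week 40; it could be none.

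**What to change.** In SAP Table 2-2, replace the Week 36 row with: Week 40, planned Study Day 280, window Study Days 273-287. Leave Week 36 in Table 2-1. No other window has to change for this point.

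This is a one-row edit before database lock. It needs no new data. The only loss is the slot for stray unscheduled laboratory or palpation values on Days 245-259, which would still be listed.

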## 2.2 Analysis sets

### 2.2.1 Full Analysis Set

The Full Analysis Set (FAS) comprises all patients to whom study treatment has been assigned by randomization. According to the intent to treat principle, patients will be analyzed according to the treatment they have been assigned to during the randomization procedure.

### 2.2.2 Safety Set

The Safety Set includes all patients who received at least one dose of study medication...

Patients will be analyzed according to the study treatment received, where treatment received is defined as the randomized treatment if the patient took at least one dose of that treatment or the first treatment received in the randomized treatment was never received.

### 2.2.3 Per-Protocol Set

Not Applicable for this prematurely terminated study.

#### **2.2.4 Pharmacokinetic analysis set**

Not Applicable for this prematurely terminated study.

#### **2.2.5 Subgroup of interest**

Not Applicable for this prematurely terminated study.

#### **2.2.6 Withdrawal of Informed Consent**

Any data collected in the clinical database after a subject withdraws informed consent from all further participation in the trial, will not be included in the analysis data sets. The date on which a patient withdraws full consent will be recorded in the eCRF.

Death events in some countries can be reported if the death event can be confirmed to be captured from public records (registers). If confirmed, the events will be included in the analysis.

Third party data e.g. PK, [REDACTED] etc., collected in the clinical database without having obtained consent for collection will not be included in the analysis data sets. These data will be excluded by the presence of the appropriate protocol deviation criterion.

